- Policlinico Umberto I Hospital, Sapienza University of Rome, Rome –Italy: [name]
- Catholic University of the Sacred Heart, Rome –Italy: [name], [name]
- University of Bari – Italy: [name]
- University of Bologna – Italy: [name]
- University of Genova – Italy: [name]
- University of Torino – Italy: [name]
- University of Vienna, Vienna – Austria: [name]
- Pitié-Salpêtrière Hospital, Sorbonne University Paris, Paris – France: [name]
- University of Maryland, Baltimore – USA: [name]
- St Vincent’s Hospital, Sydney – Australia: [name]
- Columbia University, New York – USA: [name], [name]
- Vall D’Hebron Hospital, Barcelona – Spain: [name]

Summary

Background: Over the past decade, the use of extracorporeal membrane oxygenation (ECMO) for respiratory support in adults has increased. Several trials have highlighted how red blood cells transfusion can cause several negative effects and, currently, a restrictive transfusion trigger in critically ill patients is widely accepted.

The optimal management of anticoagulation targets and transfusion practice in veno-venous-ECMO (VV-ECMO) patients is still under debate. Traditionally, the threshold for transfusions of packed red blood cells (PRBC) in ECMO is aimed at keeping hemoglobin (Hb) values in the normal range (12-14 g/dL), but some case series have shown how the Hb target can be lower, and with comparable clinical outcomes.

While there are extensive reviews on predicted ECMO survival, and management (even with many debated issues), there is a significant knowledge gap in understanding the benefits and risks of transfusions during VV-ECMO

Methods/Design: Prospective observational multicenter study. The principal aim is to describe current effective blood product usage, during VV-ECMO. The secondary aim is to describe in a large cohort of ECMO patients the current anticoagulation strategy and bleeding episodes occurrence.

The study will be conducted at a multicenter level including in each center all consecutive adult vv-ECMO patients during one year. The data collection will include pre-ECMO characteristics, transfusion strategies and blood test results during the first twenty-eight days after ECMO cannulation or until the end of ECMO support if the length is shorter, and clinical outcomes up to the end of ICU stay.

The descriptive variable end points for the primary aim will be the daily and the total amount of PRBC and other blood products (Plasma, Platelets, Fibrinogen, Antithrombin III).

The descriptive variable end points for the secondary aim will be the type and dose of anticoagulation, and episodes of bleeding according to site and severity.

Expected Results: A collaborative combination of ECMO centers will evaluate prospective data of transfusion practices during ECMO. The investigators would be able to describe the currently strategy for administration of blood products, anticoagulation and the effective incidence of bleeding episodes worldwide.

Background

Over the past decade, the use of extracorporeal Membrane Oxygenation (ECMO) for respiratory support in adults has vastly increased [1]. Veno-venous ECMO (VV-ECMO) can be initiated in case of Acute Respiratory Distress Syndrome (ARDS) as salvage therapy for patients with profound gas exchange abnormalities despite protective lung ventilation and other rescue therapies [2, 3].

Many aspects of ECMO management are still under debate despite the increasing number of cases [4, 5]. Among these debated topics there is certainly the optimal management of transfusion practice [6].

Several trials in the last decade have recognized how red blood cells transfusion can cause several negative effects, including transfusion related immune reactions, the potential transmission of diseases, the development of transfusion-related complications (such as transfusion-related acute lung injury – TRALI – or transfusion-associated circulatory overload – TACO) and immunosuppression. [7, 8] The Anemia and Blood transfusion in critical Care (ABC) study, an epidemiological survey of 3534 patients conducted in 146 ICUs of western Europe, confirmed an increased mortality rate in transfused patients [9]. On the other hand, the Sepsis Occurrence in Acutely Ill Patients (SOAP) database (n=3147) found that although there was a direct relationship between the number of blood transfusions and the mortality rate, blood transfusion was not significantly associated with a worse mortality rate [10].

Hebert and colleagues randomized 838 critically ill patients to either a liberal protocol in which transfusions were administered to maintain hemoglobin levels above 9 g/dl, or a restrictive strategy in which hemoglobin levels were kept between 7 and 9 g/dl. Overall, the 30-day mortality rate was 19 % in the restrictive group and 23 % in the liberal transfusion group (p=NS). [11]

On the other hand, anemia can also cause a potential increase in morbidity and mortality in critically ill patients, and in ECMO is an even greater critical issue in reducing delivery of oxygen (DO₂). [12, 13] Moreover, despite improvement in technology and care, complications related to ECMO are still high, and frequently involve an imbalance in the coagulation status due to anticoagulant use in the presence of coagulopathy [14-16]. Consequently, the risk of thrombosis (presumably microthrombosis) and hemorrhage remain to be high [17-20]. In the case of ongoing bleeding, transfusion of Packed Red Blood Cell (PRBC) is required to support desired haemoglobin levels [21, 22].

Traditionally, the threshold for PRBC transfusions in ECMO is aimed to maintain hemoglobin (Hb) values in the normal range (12-14 g/dL) [23]. Despite this, there is considerable uncertainty regarding the optimal haemoglobin threshold for the use of PRBC transfusions in anemic patients during ECMO support.

Prompted by the general reappraisal of PRBC transfusion use, some case series using lower target for Hb during vv-ECMO support have been published [24-26]. However, such protocols do not use/suggest a definitive trigger/target of Hb [27].

There is also some evidence that a higher number of transfusions in ECMO patients is associated with worse outcomes [28-30]. However, such a relationship is difficult to assess given the large

number of factors influencing transfusion practice in this setting: target of anticoagulation, frequent bleeding episodes, the peculiar characteristics of the circuits that can cause mechanical damage, activation of inflammation, and consumption of platelet and coagulation factors, to name but a few [31].

Moreover, most of the available data on transfusions during ECMO are heterogeneous, usually including VV-ECMO and veno-arterial-ECMO (VA-ECMO) configuration, and mixing adults with neonatal and pediatric cohorts, which are historically more represented. Recently, a meta-analysis including 1042 patients presenting refractory ARDS and focusing on complication rate and hospital mortality associated with VV-ECMO showed a limited impact of bleeding and total number of haemo-derivates administrated on patient outcome. [32]

In this context, the decision of giving a transfusion during ECMO support is still a real challenge since several parameters have to be taken into account at the same time. A strict trigger has not yet been defined in this population, and the literature on critically ill patients suggests a relevant reduction in the amount of transfusion.

Rationale for the study

Providing adequate DO₂ can be approached in several ways during vv-ECMO support, but the hemoglobin target is always a critical point, and a relevant piece of the puzzle of assuring the best oxygenation in patients affected with acute respiratory failure (ARF). There may be important variations between hospitals and countries in the use of PRBC transfusions, which may impact patient outcome. Large scale, national, and international studies are currently lacking.

While there are extensive reviews on predicted ECMO survival, and management (even with many debated issues), there is a significant knowledge gap in understanding the benefits and risks of transfusion during VV-ECMO. [30, 33, 34]

An international multicenter study will evaluate prospective observational data of transfusion practices during VV-ECMO for ARF, analyzing it in light of anticoagulation and bleeding episodes.

Aim of the study

The PROTECMO study is aimed at being a collaborative study including a large number of ECMO centers worldwide, describing, in real practice,

- 1) Incidence of major bleeding events and amount of blood product transfused
- 2) Type, trigger and level of anticoagulation adopted

The descriptive variable end points for the primary aim will be the daily and the total amount of PRBC and other blood products (Plasma, Platelets, Fibrinogen, Antithrombin III).

The descriptive variable end points for the secondary aim will be the type and dose of anticoagulation, and episodes of bleeding according to site and severity.

Study Design: international multicenter prospective observational cohort study.

For the primary outcome PRBC will be evaluated as total amount during the ECMO run and for the first 28 days as daily amount. The total amount of PRBC, adjusted for the ECMO length of stay, will be evaluated in light of pre-ECMO parameters (age, comorbidities, postoperative state and severity scores) and of daily data (bleeding episodes, ECMO blood flow, dieresis, CRRT, Hb, major events). Daily occurrence of PRBC transfusion will be described according to pre-ECMO characteristics and daily parameters (Hb, bleeding, hemodynamics, renal function, circuit change).

Plasma, platelets, Fibrinogen, Antithrombin III administration will be evaluated according to pre-ECMO data and according to daily APTT level (or other coagulation monitoring adopted), bleeding episodes, sepsis.

For the secondary outcomes type of anticoagulant will be described as well as daily dose and daily target for the parameter targeted (APTT, ACT, r-TEG, anti-Xa according to local protocol). Anticoagulation will be described in relation to pre-ECMO parameters and daily episodes of bleeding and occurrence of sepsis.

Bleeding episodes will be described according to site (airway – including tracheotomy - oro-nasal, gastric, intrathoracic, abdominal, intestinal, retroperitoneal, urinary tract, other) and classified according to severity following 5 adjusted categories of the Bleeding Academic Research Consortium (BARC) score: Type 0, no bleeding; Type 1, Any overt bleeding that requires heparin infusion rate reduction or PRBC transfusion (provided Hb drop was related to bleeding); Type 2, any overt bleeding that requires heparin infusion rate reduction and packed red blood cells transfusion or non-surgical procedure to stop bleeding (provided Hb drop was related to bleeding); Type 3, Any life-threatening bleeding that required PRBC transfusion and surgical intervention for control of bleeding or ECMO discontinuation; Type 4: any fatal bleeding.

The study is prospective and, consequently, in each center all consecutive adult patients who are eligible according to inclusion and exclusion criteria should be included in the study up to 20 patients.

Every patient included will be registered for baseline values, and will then be followed for ECMO management and transfusion management daily for the first two weeks and weekly during the following two weeks or until ECMO weaning if the ECMO run will be shorter than the observation time. During the first two weeks of observation, daily parameters will be recorded. Moreover, data will be recorded for every PRBC, Plasma, Platelets transfusion event. The patients will be observed for the clinical outcomes until they are discharged from the ICU and 6-months mortality will be recorded. Considering that according to the Extracorporeal Life Support Organization summary, the average length of respiratory ECMO run is about 12 days we believe that the majority of ECMO run will be fully covered by the observation period and, at least, it will be paradigmatic of a center's actual practice and, at the same time, will assure a considerable sample size of transfusion events.

Data will be reported according to the STROBE (Strengthening the reporting of observational studies in epidemiology) statement checklist.

The knowledge about this topic may not be achieved differently by other study design like retrospective studies or surveys. In fact, in 2017, ESICM endorsed a survey on the topic (data presented at the ECISM congress 2018) that showed a strong variability among centers about blood products transfusions, but the level of evidence achieved by a survey is low. Moreover, to explore retrospectively datasets of published studies would not allow to highlight the current practice and the strength of the study rely on the length that is one year and will surely cover the current technological frame considering a rapidly evolving scenario.

Study population: inclusion criteria/patient selection

All patients who receive extracorporeal lung support (ECMO) for ARDS respiratory causes will be included. Of note, considering the observational design of our study, patients can be included in other studies concurrently (this will be noted on the CRF).

Exclusion criteria: refusal to include

Jehovah's witnesses and all patients refusing transfusions for personal reasons will not be excluded if a valid informed consent is acquired, but they will be analyzed separately.

Study conduction

The study will be conducted in compliance with the current Helsinki Declaration and the standards of good clinical practice.

The protocol will be entered into a public database (www.clinicaltrials.gov).

Given the explorative nature of this study, the required number of patients was not calculated, but considering at least 10 patients/year for each center (considered the worst prediction) we imagine that the included patients will be at least 100 in Italy and we presume to enroll at least a double number worldwide.

Study duration

- Transfusions decisions for each patient will be recorded daily during a two-week period after ECMO cannulation and weekly for the subsequent two weeks, or until the end of ECMO support if the length is < 28 days.
- Patients will be observed until ICU discharge with a follow up to sixth months for mortality
- The inclusion period will be 12 months for each center.

Data collection methods

Data will be recorded using pre-printed CRF by the principal investigator (PI) in each center or directly they will be recorded online. All data will be reported in a centralized online and Web-based fully encrypted database (REDCAP). The study coordinator will regularly contact the local PI to ensure data collection and reporting as well as completion of patient follow-up.

Moreover the study coordinator, available at ISMETT, will keep regularly updated the local investigators on the data recorded and will help in keeping in touch with local PI or if authorized will keep in touch with eventual hospitals or other sanitary residency where the patients are transferred. In the management of the study the data manager available at ISMETT will be dedicated to the goal of reducing to the minimal the loss of data also with the follow up.

The access to the REDCAP database will be regulated by personal credentials (username and password) so that each investigator will have granted specific levels of access (read-only, data entry, or full-administrative privileges).

Every participating center will have to ask the permission to their Ethic Committee or other relevant and competent authorities according to the local rules.

Data will include clinical characteristics: baseline demographics, basic biological values (e.g., blood gas, hemoglobin), primary diagnosis, comorbidities, underlying etiology of acute respiratory failure, severity of illness (e.g., SOFA, SAPS 2), type of ECMO, and the size of the cannulas.

ECMO management data will be collected daily for the first 28 days. Additionally, fluid balance, adverse events, Hb and all hematological data, anticoagulation management and monitoring will be collected every 24 hours.

Data will also be collected for the duration of mechanical ventilation, duration of ECMO, and ICU length of stay. Clinical outcome assessment will be made, with date of death, ICU discharge, hospital discharge, sixth month mortality.

Statistical Analysis

Descriptive statistics including frequency (percentage), median and interquartile range (IQR) will describe overall population and groups of survivors and non-survivors.

In order to describe current transfusion practice the amount of PRBC, Plasma and Platelets, will be described as units and ml and as a number of transfusions adjusted for ECMO length of stay and considering the concomitant bleeding episodes.

Fibrinogen and Antithrombin III will be described as mg or units respectively and as a number of administration.

Anticoagulation will be reported as type, mean dosage and the confidence interval (CI 95%).

Hb average level and the confidence interval (CI 95%) will be reported.

Baseline categorical and continuous variables will be compared for transfusion and ECMO weaning groups. In particular categorical variables will be compared with chi-square tests and continuous variables will be compared with Student's T-test, or Wilcoxon rank-sum tests, otherwise.

Multiple COX regression analysis will be used in order to explore the impact of confounding factors such as baseline patient severity, ECMO length of stay, bleeding episodes and possible others covariates and factors that will be observed and raised relevance during the first exploratory or univariate analysis. The impact of relevant confounding factors such as length of ECMO run, pre-ECMO severity scores, pre-ECMO administration of transfusions will be analyzed separately and together in multiple analyses.

In particular daily RBC transfusion will be studied according to the association to renal function, fluid balance, worst Hb level, episodes of bleeding, use of vasopressors, ECMO blood flow.

A p-value less of than 0.05 will be considered significant. Data handling and analyses will be done with SAS 9.4 software (SAS Institute Inc, Cary, NC, USA) and R 3.3 software (R Foundation for Statistical Computing).

Patient data Collection

For each included patient the investigators will collect the following data:

1. Clinical data

- Demographics: age, gender, weight, height, BMI
- Pre-existing pulmonary disease: asthma, cystic fibrosis, chronic obstructive pulmonary disease, pulmonary hypertension, pulmonary fibrosis, chronic restrictive lung disease
- Main co-morbidities: diabetes mellitus, chronic renal failure, ischemic heart disease, heart failure, chronic liver failure, neurological impairment
- Cause of ARF: bacterial pneumonia, viral pneumonia, trauma/burns, aspiration pneumonia, pancreatitis, pulmonary vasculitis, post lung transplantation
- Diagnosis: ARDS, Chronic end stage respiratory disease
- Postoperative period < 7 days. Pregnancy or peri-partum.
- Pre-ECMO hospital/ICU length of stay, mechanical ventilation days
- Patient characteristics at ICU admission: SAPS 2, SOFA score, PaO₂/FiO₂ ratio, hematocrit, platelets
- ECMO severity scores: PRESERVE score, RESP Score, ECMOnet if appropriate

2. ECMO and daily management data

- Type of circuit: heparin-bonded or not, type of oxygenator
- Type of anticoagulation: heparin, bivalirudin, argatroban, no anticoagulant

- Dose of anticoagulation
- Amount of PRBC, Plasma, platelets transfused (unit and ml) the day before
- Eventual Fibrinogen administration (mg)
- Antithrombin III level
- Antithrombin III administration (Type: human plasma-derived, recombinant) and dosage
- Episodes of bleeding classified according to site (airway – including tracheotomy - oro-nasal, gastric, intrathoracic, abdominal, intestinal, retroperitoneal, urinary tract, other) and severity according to 5 adjusted categories of the Bleeding Academic Research Consortium (BARC) score: Type 0, no bleeding; Type 1, Any overt bleeding that requires heparin infusion rate reduction or PRBC transfusion (provided Hb drop was related to bleeding); Type 2, any overt bleeding that requires heparin infusion rate reduction and packed red blood cells transfusion or non-surgical procedure to stop bleeding (provided Hb drop was related to bleeding); Type 3, Any life-threatening bleeding that required PRBC transfusion and surgical intervention for control of bleeding or ECMO discontinuation; Type 4: any fatal bleeding
- Daily blood and air flow, ECMO FiO₂
- 24 hours diuresis and fluid balance
- Use of continuous renal replacement therapy
- Mean arterial pressure, use of vasopressors
- Septic shock
- Hemoglobin, hematocrit, platelet count, fibrinogen if available.
- Daily gas exchange: pH, PaO₂, PaCO₂, SaO₂
- Daily parameter for anticoagulation value (APTT, ACT, r-TEG, anti-Xa according to local protocol).
- Major events (cardiac arrest)
- Cannulation site complications: (bleeding or thrombosis)
- Circuit change and main cause of change (thrombocytopenia, hypofibrinogenemia, evidence of clots, membrane dysfunction, hemolysis).

3. PRBC Transfusion data (only data available according to the center practice)

- Reason for transfusion: Low Hb, Hemodynamic impairment, Low ECMO blood flow
- Hb before transfusion
- First Hb checked after transfusion.
- Presence of bleeding, type of bleeding.
- SvO₂, SaO₂, lactates, ECMO blood flow, dose of vasopressor before and after (1 hour or best possible) transfusion

4. Outcome data

- ECMO weaning yes/not
- ICU discharge yes/not and date
- Days of mechanical ventilation after ECMO weaning. Date of death
- Type of discharge: ward, another ICU, rehabilitation center, home
- 6-months status: alive/deceased

Ethics: Informed Consent and Treatment of personal data

The study will be conducted in compliance with the current Helsinki Declaration and the standards of good clinical practice.

The study involves the enrollment of patients undergoing extracorporeal membrane oxygenation support and therefore unable to express a consent.

Every participating center will have to ask the permission to their Ethic Committee or other relevant and competent authorities according to the local rules.

At ISMETT, according the Italian rules (and we strongly suggest to follow the same at the other centers), the investigators will apply the following practice about informed consent as it was approved by the Ethic Committee. All the participating centers will be supported with approval by ISMETT Ethic Committee and providing materials and translated informed consent either for the participation in the study and for the data protection policy.

According to the Authorization N. 8 of the Italian Data protection Authority (hence named “Garante della Privacy”), data and biological samples relating to individuals that cannot provide their consent because they are incapable may be used for observational studies giving all the following characteristics, as it is for our study: (i) no immediate beneficial for the patients in any case of results from the study (ii) the complete safety of procedures for the dignity and health of the enrolled patients, (iii) the lack of possibilities to perform a comparable study in an awake cohort, considering that ECMO is started in severely critically ill patients.

According to the art. 82 of the Codice Privacy the investigators will ask for a consent for the treatment of personal data of the patients that for the particular support of the ECMO are almost always sedated at least at the beginning of the ECMO running - so they have to be considered temporarily unable to express a consent - to those that have legal authority over them or to the immediate relatives or to a person cohabiting with them or – failing these – to the person in charge of the facility where the data subject is hosted. In case the patient is able to an informed consent it will be asked to himself.

In the case of following improvement of neurological condition of the patient a consent directly to the patient will be asked as soon as the patient will be considered again able to express a valid consent.

The investigators state that for the protection of privacy of the patients enrolled in the study, information and health data will be treated without identification elements and will be labeled with an alphanumeric code that will not allow to recognize the identity of the patients.

The list where there is the association between alphanumeric codes and identification data of the patients will be stored only by the principal investigator and will be used just in case of absolute necessity.

The results of the research will be diffused as aggregate data and in ways that will not allow in any case the identification of the enrolled patients.

Safety

The present study, giving its observational design, has a complete safety profile.

There will be no additional interventions or measurements other than those that are standard of care at the participating center. All clinical activity will follow the well established protocols for ECMO support at each participating center and consequently the patients are at no risk by in participating in the study.

Given the observational nature of the study, no insurance is required.

Predefined subgroup analyses

If the sample size will be adequate, as explorative analyses, we will perform some subgroup analyses according to the following predefined plan.

Exploratory analyses will stratify data for center workload (<10, 10-20, >20 ECMO run per year), according to geographical areas (we imagine a stratification among continents but we will verify if, giving the amount of data, will be reasonable a country stratification), and for pre-ECMO severity scores (Preserve score and Respscore) divided in quartiles.

Moreover, by the repeated measurements of hemoglobin and eventual transfusion event, for each center we will profile the actual and effective hemoglobin accepted as a trigger. The outcome weaning from ECMO and effective ICU discharge will be stratified also according to different hemoglobin values (<7, 7-10, >10, >12).

Another subgroups analysis will involve age, considered a major impacting factor in survival during ECMO. Patients will be divided in quartiles and patients > 60 years old will moreover evaluated.

Jehovah's witnesses and all patients refusing transfusions for personal reasons, as well as patients affected with hematological malignances will be analyzed separately.

Effective resources to implement the project

The study will be coordinated by IRCCS-ISMETT (Istituto Mediterraneo per I Trapianti e Terapie ad alta specializzazione).

Throught the REDCAP database, data will be collected and then analyzed at ISMETT.

The study has received the endorsement of the European Society of Intensive Care Medicine (ESICM) and the International ECMO network.

Professional statisticians and data manager at ISMETT will work on the project assuring proper data handling and performing the interim and final analyses.

No financial support is currently available.

Expected results, potential benefit of the study and publication program

A collaborative combination of ECMO centers will evaluate prospective data of transfusion practices during ECMO. The investigators would be able to describe the currently strategy for administration of blood products, anticoagulation and the effective incidence of bleeding episodes worldwide. Giving the lack of knowledge on the field, it will be valuable to attempt to find some evidence from actual clinical practice.

The promoter of the study, in accordance with the Note of the Italian Ministry of health n 6, 02 September 2002, will shortly publish the results of the Study, as soon as they are sent by every participating center, and anyway within 12 months after the completion of the study. Data will be published in a relevant journal in the field of intensive care medicine.

In each center two principal investigators will be involved, acknowledged as collaborators and listed in pubmed. The minimal number of patient recruited during one year will be 10 for each investigator. Some of the national coordinators, according to the entity of data and type of journal will be listed as authors.

References

2. Lewandowski K, (2000) Extracorporeal membrane oxygenation for severe acute respiratory failure. *Critical care (London, England)* 4: 156-168

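### The primary PRBC outcome needs a whole-run total and daily amounts to day 28, but the stated recording schedule turns weekly after day 14 and stops at day 28

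*Combined protocol and SAP*

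**What the plan says.** **Outcome.** Study Design defines the primary PRBC outcome over two windows: "For the primary outcome PRBC will be evaluated as total amount during the ECMO run and for the first 28 days as daily amount". It adds that "Daily occurrence of PRBC transfusion will be described according to pre-ECMO characteristics and daily parameters", naming Hb, bleeding, hemodynamics, renal function and circuit change. Aim of the study also lists daily and total amounts of plasma, platelets, fibrinogen and antithrombin III.

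**Weekly after day 14.** Study Design follows ECMO and transfusion management "daily for the first two weeks and weekly during the following two weeks or until ECMO weaning". It also says: "During the first two weeks of observation, daily parameters will be recorded". Study duration agrees: "Transfusions decisions for each patient will be recorded daily during a two-week period after ECMO cannulation and weekly for the subsequent two weeks".

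**End at day 28.** The Summary limits collection to "transfusion strategies and blood test results during the first twenty-eight days after ECMO cannulation or until the end of ECMO support" if that comes sooner. Study duration has the same end point.

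**Daily to day 28.** Data collection methods says ECMO management data are collected on each of the first 28 days, and that Hb, other hematological data and fluid balance are collected every 24 hours. In Patient data Collection, the PRBC amount sits in item 2, whose heading covers ECMO and daily management data.

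**Amount field and event records.** The PRBC, plasma and platelet amount in item 2 (units and ml) refers to the preceding day. Study Design adds that "data will be recorded for every PRBC, Plasma, Platelets transfusion event", with no time window. The event items in item 3 cover PRBC only, are limited to what each center's practice makes available, and list neither units nor ml.

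**The concern.** Describing how much blood product is given is the study's principal aim, so the schedule has to deliver the amounts that the outcome is built from. As written it does not:

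- A weekly form that asks about one preceding day cannot supply daily amounts for days 15–28, nor a complete total for a run that goes past day 14.
- Recording that closes at day 28 cannot supply a whole-run total for a longer run, even if it is daily until then.
- The daily covariates are split in the same way. One section places daily parameters in the first two weeks, and another has Hb and fluid balance every 24 hours.
- Fibrinogen and antithrombin are outside the event-recording sentence, so nothing backs up their totals after day 14 under the weekly schedule.

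The long runs lose data, so the total would be understated most where ECMO lasts longest. The planned adjustment for ECMO length of stay adds to this. The text does not say whether it is a ratio, an offset or a covariate, or whether it uses full-run or observed days. Dividing a truncated numerator by full-run days would understate the rate.

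**Working it through.** The plan gives no sample-size or precision calculation to reproduce. The check is a day count taken from the text, followed by an illustration of size.

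**1. Day count under the weekly schedule.** Daily forms cover days 1–14. Two weekly forms cover days 15–28, each giving one preceding day.
- Daily amounts available: 14 + 2 = 16 of 28.
- Days with none: 28 − 16 = 12, which is 12/28 = 43% of the window and 12/14 = 86% of days 15–28.
- Daily recording to day 28, as Data collection methods implies, would give 28 of 28.

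**2. Single runs.**
- 28-day run, weekly schedule, no event amounts: 1 − 16/28 = 43% of days uncaptured.
- 40-day run, same conditions: 1 − 16/40 = 60%.
- 40-day run, complete to day 28 and then nothing: 1 − 28/40 = 30%.

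**3. Size across a cohort (illustration).** From Study Design: an average run of about 12 days. Assumed, because the documents give no spread: six run-length shapes with mean 12, and a constant PRBC rate.

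The share of ECMO days after day t is S(t) = ∫ from t to ∞ of P(T > u) du, divided by 12. Three cases follow:
- A: event records carry amounts to decannulation. Missed = 0.
- B: complete to day 28, then nothing. Missed = S(28).
- C: event records carry no amounts, and weekly forms give one day in seven. Missed = S(14) − [S(14) − S(28)]/7.

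Worked example, exponential: S(14) = e^(−14/12) = 0.311 and S(28) = e^(−28/12) = 0.097. So C = 0.311 − 0.214/7 = 0.281.

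| Shape (mean 12) | Runs past day 14 | Runs past day 28 | B: total missed | C: total missed |
|---|---|---|---|---|
| Exponential | 31.1% | 9.7% | 9.7% | 28.1% |
| Lognormal, CV 1 | 27.4% | 7.6% | 9.7% | 24.7% |
| Lognormal, CV 1.3 | 25.7% | 8.9% | 15.5% | 30.8% |
| Gamma, CV 0.7 | 32.3% | 5.2% | 3.0% | 18.2% |
| Gamma, CV 0.5 | 31.5% | 1.7% | 0.6% | 11.5% |
| Gamma, shape 0.75 | 30.1% | 11.2% | 14% | 32.9% |

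The plan's remark that most runs will be fully covered is consistent with this table: about 89–98% end by day 28. That does not give a whole-run total for the rest.

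**4. Length-of-stay adjustment.** Suppose the adjustment is a ratio and the rate is constant at r per day. A 40-day run recorded to day 28 then gives 28r/40 = 0.70r with full-run days, an understatement of 30%. With observed days it gives 28r/28 = r. The total remains incomplete either way.

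**The case against.** The strongest reply is event recording. Study Design says every PRBC, plasma and platelet event is recorded, and Statistical Analysis plans to report these products in units, in ml and as a number of transfusions. The CRF is not in the documents and may hold event amounts to decannulation. The sentences that end at day 28 speak of transfusion strategies and decisions, not of amounts. If the event records do hold amounts throughout, the PRBC loss is zero. This stands as a possibility, and it is why no single size can be given. The text does not secure it: no window is stated, no units or ml are listed, fibrinogen and antithrombin are left out, and event records give no covariates on days without transfusion.

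A second reply is that the study is descriptive, most runs are short, and the plan openly expects full coverage only for the majority. That limits the weight of the point. It does not reconcile an outcome defined over the whole run with recording that stops earlier.

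A reader might also infer three stronger things that the documents do not support:
- That centers would follow different schedules and so appear to differ in practice. Data collection methods describes a pre-printed CRF, one central REDCAP database, a coordinator in regular contact and a dedicated data manager. An implemented form would probably set one schedule for all.
- That the per-center Hb-trigger profile would be distorted. It draws on Hb measurements and transfusion events, and the event items include the Hb before transfusion, so form frequency matters much less there.
- That totals will be compared between weaning groups. Statistical Analysis plans only baseline comparisons for those groups.

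**Conclusion.** The inconsistency is established from the text alone. Following the stated weekly schedule and the only listed amount field gives at most 16 of 28 daily PRBC amounts. Recording that ends at day 28 leaves the whole-run total incomplete for longer runs. That daily collection to day 28 extends to PRBC amounts is an inference from the item 2 heading; its conflict with the weekly schedule for ECMO management data is explicit.

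The size of the loss is not established. On an average run of about 12 days, a constant rate and assumed shapes, 26–32% of runs pass day 14 and 2–11% pass day 28. The share of the PRBC total missed lies between 0% and about 31% (33% under the gamma shape 0.75), depending mainly on whether event records carry amounts. It would be wrong to read the upper figure as an expected loss, or to conclude that the primary outcome cannot be recovered. This should be fixed because the protocol as written does not guarantee its own primary outcome and the repair is modest.

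**What to change.** State one recording schedule across the Summary, Study Design, Study duration and Data collection methods. Any of these would do:

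- **(a)** Record the amount for each ECMO day, or for each event with units and ml, to decannulation. This serves both the daily and the total outcome.
- **(b)** Keep weekly forms after day 14, add a field for the cumulative amount since the previous form and a closing form at the end of ECMO, and limit the daily-amount outcome to days 1–14.
- **(c)** Restate the PRBC total as days 1–28, with complete capture in that window.

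Apply the same capture window to the plasma, platelet, fibrinogen and antithrombin totals. State the window over which daily covariates are recorded, and match the daily PRBC description to it. State how the length-of-stay adjustment is made, and use observed ECMO days rather than full-run days wherever the numerator is truncated.

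**Cost.** Protocol wording and a form change, which may already be partly in place in the CRF. Options that add capture need more chart abstraction for runs over 14 days. With at least 200 patients (at least 100 in Italy and at least double that worldwide), this is at least about 200 × 0.257 = 51 to 200 × 0.323 = 65 patients on the assumed shapes. Ethics notification may be needed at each center, and the study reports no financial support. No extra patients or procedures are needed. Option (c) costs least if capture to day 28 is already complete, but gives up the whole-run total.
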